18.8. CONFIDENTIALITY OF STUDY DOCUMENTS AND PATIENT RECORDS

The investigator must ensure anonymity of the patients; patients must not be identified by names in any documents submitted to Minapharm. Patient enrollment log must be kept strictly confidential to enable patient identification at the center.

Table 10	Mean changes in Activated Partial Thromboplastin Time (APTT) where it will be done before first dose, 4 & 8 hours after first dose then on days 1,8,15 post operatively.....	18
Table 11	Proportion of patients experienced major bleeding	19
Table 12	Number and percent of Adverse Event among treatment groups	20
Table 13	Number and percent of Serious Adverse Event among treatment groups	20
Table 14	Percent Change in mean Hb%	21
Table 15	Percent Change in mean Platelets count	21
Table 16	Percent Change in mean Systolic BP.....	22
Table 17	Percent Change in mean Diastolic BP	22
Table 18	Percent Change in mean Sitting Pulse Rate	23
Table 19	Percent Change in mean Oral Temperature	23
Table 20	Number and percent of causes of treatment discontinuations	24
Table 21	Number and percent of Concomitant medication	25

1 Introduction:

1.1 Background:

Hirudin is the most potent naturally-occurring direct thrombin inhibitor (DTI), and the first parenteral anticoagulant used on humans. ⁽¹⁾

Originally derived from the medicinal leech (*Hirudo medicinalis*), it consists of a 65 amino acids polypeptide chain, forming non-covalent, equimolar, non-reversible 1:1 complexes with α thrombin. ⁽¹⁾ When hirudin-bound, thrombin-catalyzed reactions and fibrinogen clotting are blocked, and coagulation is subsequently inhibited. ⁽²⁾ Hirudin was previously produced in limited amounts, however, recombinant DNA technology allowed its mass production. ⁽³⁾ These recombinant forms bind bivalent to thrombin with pharmacokinetic and anticoagulant profile similar to that of the native form. ⁽⁴⁾

Recombinant Hirudin is a direct inhibitor of thrombin. It binds in 1:1 ratio with thrombin thus blocking the coagulation cascade and the formation of thrombi. ⁽⁵⁾

Unlike heparins, the action of Hirudin is totally independent from any coagulation cofactor that may interfere or alter its action. ⁽⁵⁾

Thrombexx is useful in the prevention of thromboembolic complications in at risk patients thrombexx (15 mg) is administered by subcutaneous injection 5-15 minutes before orthopedic or general surgery (after induction of regional block anesthesia) then 15 mg twice daily for 9-12 days and in bedridden patients until patient is fully ambulant (maximum 12 days) ⁽⁵⁾

According to the FDA Therapeutic Equivalence Evaluation, 30th Edition, the biosimilar of recombinant hirudin, Desirudin is FDA approved, therefore, the same applies to recombinant hirudin in Egypt.

1.2 Study Rationale

The purpose of this study is to conduct several investigations required to evaluate the efficacy and safety of subcutaneous Thrombexx ampoules in the prophylaxis of Deep Vein Thrombosis (DVT) post major orthopedic operations

2 Study Design

A Prospective, Single- Center, Phase IV Interventional, Single Arm conducted in Egypt to assess the efficacy and safety of patients undergoing major orthopedic operations such as Total knee & hip Arthroplasty with complete data and who had 2 weeks follow-up.

This study will be conducted through main phases, preoperative phase which will be as a screening visit, operative phase which is the surgery will be done and a total of 3 follow-up visits which is the postoperative phase.

1. Pre-operative phase
2. Operative phase
3. Post-operative phase (follow-up)

Detailed descriptions of the study design are as follows:

2.1 The Pre-Operative Phase

During this phase, patients will be screened for fulfillment of the inclusion and exclusion. Patient's demography, history of diseases will be collected, laboratory investigations such as Hemoglobin count, Platelets count, Activated Partial Thromboplastin Time (APTT), INR, SGPT, SGOT, Serum albumin, serum Bilirubin, serum creatinine and random blood glucose and pregnancy test for females in childbearing period

APTT should be done before IMP administration, in addition to the patient's data of Thrombexx® administration regimen decided by the treating investigator according to the standard clinical practice or as prescribed in the usual manner in accordance with the terms of the local marketing authorization with regards to dose, population and indication (and within the approved label).

Medical history and Medication history should also be collected.

2.2 The Operative Phase

During this phase, patient's registries for the type of surgery done, Type of anesthesia, patient position and type of prosthesis, & blood transfusion during surgery should be recorded. And IMP dispensing 6 hours after surgery or upon adequate hemostasis will be done. APTT will be done 4 & 8 hours after the first dose

2.3 The Follow-Up Phase

During this phase which is approximately 15 days, PE (Pulmonary Embolism) which is confirmed by spiral CT chest, any new DVT appears also to be confirmed by Doppler ultrasound, Bleeding assessment, APTT will be done on days 1, 8 & 15, concomitant medications, Hospital stay and any adverse event data will all be recorded

3 Study Objective:

3.1 Primary Objectives:

- To evaluate the efficacy of Subcutaneous Thrombexx® ampoules (r-Hirudin RB variant 15 mg) in DVT prophylaxis post major orthopedic operations

3.2 Secondary Objectives:

- To evaluate the safety of Subcutaneous Thrombexx® ampoules (r-Hirudin RB variant 15 mg) in DVT prophylaxis post major orthopedic operations in terms of serious bleeding.
- Predictive factors; baseline characteristics, Thrombexx® dose, duration and concomitant medications.
- Study population demographics and characteristics.

4 Study Outcome Measures:

4.1 Primary Endpoints:

- Primary end points included new onset symptomatic thrombosis requiring medical or surgical intervention or death due to thrombosis defined as fatal PE, ischemic stroke, mesenteric thrombosis, or myocardial infarction.
- The number of clinical PE events will be measured by spiral CT
- Mean changes in APTT where it will be done before first dose, 4 & 8 hours after first dose then on days 1,8,15 post operatively

4.2 Secondary Endpoints:

- **Major Bleeding:** was defined as clinically evident hemorrhage associated with a hemoglobin decrease ≥ 2 g/dL that leads to a transfusion of ≥ 2 units of whole blood or packed red cells outside of the perioperative period (time from the start of the surgery or procedure and up to 12 hours after), or hemorrhage that is intracranial, retroperitoneal, or into a prosthetic joint.

- Number of any reported (AE) or (SAE) during the study duration.

5 Study Population

This is a prospective study, it is important to have a well-defined study population in place prior to the start of the study. Study populations should be defined using specific inclusion and exclusion criteria, which will be used to evaluate a potential subject's ability to participate in the study.

5.1 Recruitment strategy:

It is essential that the recruitment process take into account factors that will optimize the type and number of participants enrolled in the study while minimizing time and expense. Failure to meet target accrual goals can affect the "power" of a study, making it less successful in providing quality results.

Recruitment plan will be through explaining to patients the clinical trial objective in Alexandria University hospital; referral also will be used to increase the flow rate of recruitment.

5.2 Inclusion Criteria:

Subjects meeting all of the following criteria will be considered for enrolment in the study:

1. Patients aged 18 years of age or older
2. Body Weight >60 kg
3. Patients undergoing major orthopedic operations Total knee & hip Arthroplasty
4. Patients ready to sign (ICF)
5. Patients should discontinue any agents that affect haemostasis prior to the study medication use unless strictly indicated. These agents include medications such as: anticoagulants, thrombolytics, non-steroidal anti-inflammatory agents (including Ketorolac tromethamine), preparations containing aspirin, systemic salicylates, ticlopidine, dextran 40, clopidogrel, other anti platelet agents including glycoprotein IIb/IIIa antagonists or systemic glucocorticoids.

5.3 Exclusion Criteria:

Subjects presenting with any of the following will not be included in the study:

1. Subjects with a history of hypersensitivity to any of the active ingredients of the treatments used
2. Significant bleeding injury such as solid organ laceration or intracranial bleed at discretion of attending physician
3. Hypersensitivity to Hirudin or prior documented allergy to its components
4. Pregnant or breast feeding females
5. Hemorrhagic stroke in preceding 3 months
6. Abnormal baseline coagulation characterized by an INR >1.4, obtained at the discretion of the treating clinician
7. Required therapeutic anticoagulation for atrial fibrillation, prior VTE, or mechanical heart valve
8. Treatment with concomitant anti-platelet agent other than aspirin 326 mg or more daily
9. Subjects with a life expectancy less than 1 month

6 Assessment Schedule

Subjects will be enrolled for duration of 1 months including the screening visit

- a. Preoperative phase (screening visit)
- b. Operative phase (Day 0)
- c. Visit 2: Post-operative phase (Follow-up 1(Day 1)
- d. Visit 3: Follow-up 2 (Day 8)
- e. Visit 4: Follow-up 3/ End of Study (Day 15)

7 Medicinal Products:

- Thrombexx Ampoules (r-Hirudin 15mg/ ml pro inject **S.C. only**)

8 Statistical Methodology:

8.1 Determination of Sample Size:

Sample size: Records for 100 patients who underwent major orthopedic surgery collected from 1 site

The sample size is based on literature review for previous studies, and a sample of 168 patients will be sufficient to detect an incidence of 12.5% of DVT with an acceptable error of 5%, and a 95% confidence level

8.2 Analyses variables

8.2.1 Primary analysis variables:

- Proportion of patients experienced new onset symptomatic thrombosis
- The number of clinical PE (Pulmonary Embolism) events will be measured by spiral CT

8.2.2 Secondary analysis variables:

- Number of adverse events recorded
- Proportion of patients experienced major bleeding

8.2.3 Statistical Method:

Descriptive analysis:

All statistical tests used a significance level of $P=0.05$, two tailed tests were performed for all analyses used statistical testing.

Descriptive analysis for quantitative data will include count, mean with 95% CI, standard deviation, median, minimum and maximum. For qualitative categorical variables; frequency and percentage and 95% confidence interval will be applied.

8.2.4 Interim analysis

Not applicable in this Prospective study

9 Results:

9.1 Screening Visit

9.1.1 Demographic Data and Vital Signs

9.1.2 Physical Examination

9.1.3 Medical history

9.1.4 Prior Concomitant Medication

9.1.5 Lab Results

9.2 Primary End Point:

9.3 Secondary End Point:

9.4 Study Discontinuation

9.5 Concomitant Medication

9.1 Screening Visit

9.1.1 Demographic Data and vital signs

Table 1 Demographic Data and vital signs at baseline visit

	N = 100
Gender (male), N (%)	
Age (Yrs.), Mean \pm SD, (Yrs)	
Pulse, mean \pm SD, (beats /min)	
Systolic BP, mean \pm SD, (mmHg)	
Diastolic BP, mean \pm SD, (mmHg)	
Oral Temp, mean \pm SD, ($^{\circ}$C)	

9.1.2 Physical Examination

Table 2 *Number and percent of Physical Examination at baseline visit*

		N = 100
Physical Examination	Normal, N (%)	
	Abnormal, N (%)	
If abnormal, please describe with details	Examination 1, N (%)	
	Examination 2, N (%)	
	Examination 3, N (%)	

Table 3 *Number and percent of Main Complaint at baseline visit*

		N = 100
Main Complaint	Hip, N (%)	
	Knee, N (%)	

9.1.3 Medical History

Table 4 *Number and percent of medical history at baseline visit*

	N = 100
Medical History, N (%)	
Med history 1, N (%)	
Med history 2, N (%)	
Med history 3, N (%)	

9.1.4 Prior Concomitant medication

Table 5 *Number and percent of Prior Concomitant medication at baseline visit*

	N = 100
Prior Concomitant medication, N (%)	
Prior ConMed1, N (%)	
Prior ConMed2, N (%)	
Prior ConMed3, N (%)	

9.1.5 Lab Results

Table 6 Mean of Lab Results at baseline visit

	N = 100
Was the lab report received? N (%)	
Hb%, Mean ± SD, (g/dL)	
Platelets Count, Mean ± SD, (x10³/μL)	
APTT, Mean ± SD, (seconds)	
INR, Mean ± SD	
SGPT, Mean ± SD, (IU/L)	
SGOT, Mean ± SD, (IU/L)	
Sr. Albumin, Mean ± SD, (g/dL)	
Sr. Bilirubin, Mean ± SD, (mg/dL)	
Sr. Creatinine, Mean ± SD, (mg/dL)	
Creatinine Clearance, Mean ± SD, (ml/min)	
RBS, Mean ± SD, (mg/dL)	

Table 7 *Number and percent of Surgery Information*

		N = 100
Type of Surgery	Surgery 1, N (%)	
	Surgery 2, N (%)	
	Surgery 3, N (%)	
Type of Anesthesia	Anesthesia 1, N (%)	
	Anesthesia 2, N (%)	
	Anesthesia 3, N (%)	
Patient Position	Position 1, N (%)	
	Position 2, N (%)	
	Position 3, N (%)	
Type of prosthesis	Prosthesis 1, N (%)	
	Prosthesis 2, N (%)	
	Prosthesis 3, N (%)	
Blood Transfusion	Transfusion 1, N (%)	
	Transfusion 2, N (%)	
	Transfusion 3, N (%)	

9.2 Primary End Point

Table 8 *Proportion of patients experienced new onset symptomatic thrombosis*

		Follow-up 1 (Day 1)	Follow-up 2 (Day 8)	Follow-up 3/ End of Study (Day 15)	p-value
Was a Routine bilateral compression Doppler done?	Yes, N (%)				
	No, N (%)				
If “No”, please indicate a reason	Reason 1, N (%)				
	Reason 2, N (%)				
	Reason 3, N (%)				
Is the report interpreted, signed & dated by the PI or any of the designated site staff?	(Yes), N (%)				
	(No), N (%)				
If “No”, please indicate a reason:	Reason 1, N (%)				
	Reason 2, N (%)				
	Reason 3, N (%)				
If “Yes”, the report interpretation shows that the subject is:	Normal, N (%)				
	Abnormal, N (%)				
If abnormal, please state the reason:	Reason 1, N (%)				
	Reason 2, N (%)				
	Reason 3, N (%)				

Table 9 *The number of clinical PE (Pulmonary Embolism) events will be measured by spiral CT*

		Follow-up 1 (Day 1)	Follow-up 2 (Day 8)	Follow-up 3/ End of Study (Day 15)	p-value
Was a Spiral CT done?	Yes, N (%)				
	No, N (%)				
If “No”, please indicate a reason	Reason 1, N (%)				
	Reason 2, N (%)				
	Reason 3, N (%)				
Is the report interpreted, signed & dated by the PI or any of the designated site staff?	(Yes), N (%)				
	(No), N (%)				
If “No”, please indicate a reason:	Reason 1, N (%)				
	Reason 2, N (%)				
	Reason 3, N (%)				
If “Yes”, the report interpretation shows that the subject is:	Normal, N (%)				
	Abnormal, N (%)				
If abnormal, please state the reason:	Reason 1, N (%)				
	Reason 2, N (%)				
	Reason 3, N (%)				

Table 10 *Mean changes in Activated Partial Thromboplastin Time (APTT) where it will be done before first dose, 4 & 8 hours after first dose then on days 1,8,15 post operatively*

		Before 1 st dose	After 1 st dose		Post-operative			p- value
			4 h	8 h	Day 1	Day 8	Day 15	
Was an APTT test performed?	Yes, N (%)							
	No, N (%)							
If “No”, please indicate a reason	Reason 1, N (%)							
	Reason 2, N (%)							
	Reason 3, N (%)							
If “Yes”, the test result is	APTT; Mean ± SD (sec)							
APTT, % change								
p-value								
The test interpretation shows that the subject is:	Normal, N (%)							
	Abnormal, N (%)							
If abnormal, please state the reason:	Reason 1, N (%)							
	Reason 2, N (%)							
	Reason 3, N (%)							

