9.4 Study Discontinuation

Table 20 Number and percent of causes of treatment discontinuations

		N = 100	p-value
Did the patient complete the study as per protocol?	Yes, N (%)		
	No, N (%)		
Reason for the discontinuation from study	Patient Withdrew Voluntarily		
	Adverse Event		
	Lost Follow-up		
	Death		
	Other Reasons		

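### The SAP's primary tables (8 and 9) carry a between-visit p-value in one cohort but no cumulative proportion of patients affected and no 95% CI

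*SAP*

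**What the plan says.** The design is "A Prospective, Single- Center, Phase IV Interventional, Single Arm conducted in Egypt" (SAP section 2), with "Records for 100 patients who underwent major orthopedic surgery collected from 1 site" (SAP 8.1). SAP 8.2.1 names two primary variables: the proportion of patients with new symptomatic thrombosis, and the number of clinical PE events.

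The method section, SAP 8.2.3, is headed as descriptive. It states: "For qualitative categorical variables; frequency and percentage and 95% confidence interval will be applied". It also sets a 0.05 level and adds that "two tailed tests were performed for all analyses used statistical testing", without naming any test or null hypothesis.

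The shells for the primary variables are Tables 8 and 9 in SAP 9.2. Table 8 is titled "Proportion of patients experienced new onset symptomatic thrombosis". In both, the columns are Day 1, Day 8, Day 15 and p-value. The only outcome row asks whether "the report interpretation shows that the subject is" normal or abnormal at each visit. There is no overall column or row and no CI.

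Table 11 (major bleeding) has the same visit layout with a p-value. Tables 12 and 13 (adverse events) and Table 20, "Number and percent of causes of treatment discontinuations", have a p-value beside a single N = 100 column.

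**The concern.** The primary variable is one yes/no per patient over 15 days. The table meant to report it breaks the follow-up into three visits and attaches a p-value. In a single-arm trial with no stated reference rate, the only comparison in that layout is Day 1 against Day 8 against Day 15 in the same people. Equality across visits is not the efficacy question. A high event rate spread evenly over the visits would look the same as a low one.

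The result also depends on rules the SAP leaves open. It does not say whether a clot found on Day 1 is counted again on Days 8 and 15. DVT is a listed stopping rule in the protocol synopsis, and the SAP does not say how patients who stop enter the later columns.

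At stake is how the primary table will be read. A large p-value invites the conclusion that thrombosis did not increase on treatment, and a small one invites the opposite. Meanwhile the quantity that answers the objective, the incidence with its CI, has no place in the table.

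**Working it through.** **Inputs from the documents.** N = 100, one arm, assessments on Days 1, 8 and 15, two-sided 0.05. The sample-size inputs are an incidence of 12.5%, an error of 5 points and 95% confidence, giving 168 (SAP 8.1). Protocol 4.2 cites a 7% overall DVT rate on desirudin in a hip-replacement trial.

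**Assumed.** The number of DVTs in this trial and the visit at which each is first found.

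**Step 1: the plan's own figure.** n = 1.96² × 0.125 × 0.875 / 0.05² = 168.06, so 168 reproduces. This is the formula for the width of a CI around one proportion. The trial is therefore sized on precision. (That the plan enrols 100 is a separate matter.)

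**Step 2: the between-visit p-value.** Cochran's Q for k = 3 visits is Q = (k − 1)(k ΣG² − T²) / (kT − ΣL²). G are the visit totals, L the patient totals and T the grand total. With 2 degrees of freedom, p = exp(−Q/2). Take 7 DVTs first found 2/2/3:

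- *Each counted once, all 100 patients kept.* G = 2, 2, 3; T = 7; ΣL² = 7. Q = 2(3 × 17 − 49)/(21 − 7) = 0.286, p = 0.87.
- *Carried forward.* G = 2, 4, 7; T = 13; ΣL² = 2 × 9 + 2 × 4 + 3 × 1 = 29. Q = 2(3 × 69 − 169)/(39 − 29) = 7.6, p = 0.022.
- *Affected patients leave, complete cases only.* The 4 patients found on Days 1 and 8 drop out, leaving 96 with G = 0, 0, 3; T = 3; ΣL² = 3. Q = 2(27 − 9)/(9 − 3) = 6.0, p = 0.0498.

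Treating the carried-forward counts as three independent samples (Pearson chi-square) gives p = 0.22, so the choice of unnamed test matters as well.

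**Step 3: how general is this?**

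| DVTs first found (Day 1/8/15) | Counted once | Carried forward |
|---|---|---|
| 1/1/1 | p = 1.00 | p = 0.22 |
| 1/3/3 | p = 0.56 | p = 0.011 |
| 4/4/4 | p = 1.00 | p = 0.0025 |
| 7/0/0 | p = 0.0009 | p = 1.00 |
| 0/0/7 | p = 0.0009 | p = 0.0009 |

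Over all possible splits, unweighted, these two conventions fall on opposite sides of 0.05 in 1 of 10 splits for 3 DVTs, 25 of 36 for 7, and 45 of 91 for 12.

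**Step 4: does the p-value track efficacy?** No. Counted once, equal splits of 12, 30 or 60 DVTs in 100 patients all give p = 1.00.

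**Step 5: the promised quantity.** The Clopper-Pearson limits for 7/100 are the 2.5% point of Beta(7, 94) and the 97.5% point of Beta(8, 93): 7.0% (2.9 to 13.9). This is the same whether clots are counted once or carried forward. It does need a stated denominator: restricting to complete cases would give 3/96 = 3.1%.

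**The case against.** A reader might infer that the plan intends to judge efficacy by the p-value in place of the CI. The documents do not support that. No success criterion is attached to any p-value, 8.2.3 is headed descriptive, and its promise of a CI stands. The shells are abbreviated throughout: no table shows a CI, and the continuous tables show only mean ± SD although 8.2.3 also promises median, minimum and maximum. The p-value column looks like template residue, since Tables 12 and 13 refer to treatment groups in a one-arm trial. The between-visit reading is itself an inference from the layout.

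The illustration can also be challenged. The 7% is all DVT in a per-protocol hip-replacement population, whereas the primary variable is symptomatic thrombosis, and the other study cited in protocol 4.2 reported no primary events. With few events the conventions seldom disagree. The words new onset favour counting each clot once.

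Finally, protocol 15.1 plans patient-level listings, so the cumulative proportion and its CI can still be computed.

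All of this stands, and it limits the severity. It does not give the p-value a hypothesis. Nor does it put the proportion or its CI into the primary tables. The 12.5% in the sample-size statement does not fill the gap either: it enters a precision formula and is nowhere set as a value to test against.

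**Conclusion.** The point holds as a fault in the reporting shells. Tables 8 and 9, filled in as drawn, would show an uninterpretable p-value and omit the per-patient proportion with the CI that 8.2.3 promises and the sample size presupposes.

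In the example, the same 7 patients give p = 0.87, 0.022 or 0.0498 depending on an unstated counting rule, against a single 7.0% (2.9 to 13.9) when all 100 patients are in the denominator. The event counts and timings are assumptions. The flip is not universal and is rare with about 3 events.

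Because no decision rule depends on the p-value, the consequence is a misleading primary table and not a wrong formal conclusion. It should be fixed before the tables are produced, but it does not undermine the trial's data.

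**What to change.** 1. Delete the p-value columns from Tables 8 and 9. Delete them also from Table 11 (same visit layout) and from Tables 12, 13 and 20 (a single N = 100 column with nothing to compare).
2. In Tables 8 and 9, and in Table 11 for major bleeding, add one row: patients with at least one event meeting the SAP section 4 definition by Day 15, as n/N, % (exact 95% CI). The row must use that definition, because the present Doppler normal/abnormal row records neither symptoms nor intervention, nor the fatal events in 4.1.
3. State that N includes patients who stop early or miss a scan, and how their outcome is classed.
4. Label the visit columns as first detected, so that a persisting clot is not counted again.
5. State in 8.2.3 that no hypothesis test is done on the primary variables listed in 8.2.1. APTT is listed as a primary endpoint in 4.1 but not in 8.2.1, so Table 10 is not affected.

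The cost is SAP wording and table shells, with no change to data collection. The only loss is p-values that have no interpretable null hypothesis.

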5. STUDY OBJECTIVES

5.1. Primary Objectives

To evaluate the efficacy of Subcutaneous Thrombexx® ampoules (r-Hirudin RB variant 15 mg) in DVT prophylaxis post major orthopedic operations

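### SAP Table 8 carries the primary variable's title but tabulates Doppler results by visit, and no shell or derivation rule yields the patient-level primary proportion

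*SAP*

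**What the plan says.** **Endpoint.** SAP 4.1 lists as its first primary endpoint "new onset symptomatic thrombosis requiring medical or surgical intervention or death due to thrombosis", followed by "defined as fatal PE, ischemic stroke, mesenteric thrombosis, or myocardial infarction". A separate item reads "The number of clinical PE events will be measured by spiral CT".

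**Analysis variable.** SAP 8.2.1 shortens the first item to "Proportion of patients experienced new onset symptomatic thrombosis". SAP 8.2.3 says categorical variables will be given as a frequency and percentage with a 95% confidence interval.

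**Table 8 (SAP 9.2).** The title is the 8.2.1 variable. The rows are:
- "Was a Routine bilateral compression Doppler done", with reasons if not;
- whether the report was interpreted and signed, with reasons if not;
- if it was, "the report interpretation shows that the subject is" Normal or Abnormal;
- reasons if abnormal, left unspecified.

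The columns are Day 1, Day 8, Day 15 and a p-value.

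**The scan.** The Protocol Synopsis says every patient had a routine bilateral Doppler. Protocol 7.2 lists it at each follow-up visit as routine and also as confirmation of DVT. Protocol 6.3 and SAP 2.3 describe Doppler as confirming a new DVT when one appears.

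**Objective and sizing.** Protocol 5.1 sets out to evaluate efficacy "in DVT prophylaxis post major orthopedic operations". SAP 8.1 calls 168 patients "sufficient to detect an incidence of 12.5% of DVT" with 5% error and 95% confidence.

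**The concern.** The table that is meant to carry the main efficacy result measures something other than its title. An abnormal scan in a patient without symptoms would be counted under a symptomatic-thrombosis heading. A death from stroke, myocardial infarction or mesenteric thrombosis would have no row. Three visit columns without a patient total do not give a proportion of patients.

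The trial has one arm and a descriptive analysis, so the reported proportion is in effect the conclusion. If the definition is not settled before the data are analysed, either the symptomatic events or the scan findings could be presented as primary, and a reader could not tell which.

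**Working it through.** **1. Title against content.**

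| Element needed for the SAP 4.1 / 8.2.1 variable | In Table 8? |
|---|---|
| Symptomatic status | No |
| Medical or surgical intervention | No |
| Death due to thrombosis, by cause | No |
| Patients with at least one event by Day 15 | No, visit columns only |
| 95% CI (promised in 8.2.3) | No |
| Base of all analysed patients | Not stated; Normal/Abnormal applies only where the report was signed |

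The first five gaps remain whether the scan is read as routine for all (Synopsis) or as confirming an apparent DVT (Protocol 6.3, SAP 2.3).

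**2. Do other shells fill the gap?** All 21 table bodies are in the text, so removed pages do not explain it. Table 9 is spiral CT by visit, Table 10 is APTT and Table 11 is bleeding and transfusion. Tables 12 and 13 are AE and SAE lists with N = 100 and unspecified terms. Table 20 has death only as a reason for discontinuation. None combines the components per patient.

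**3. What the sizing basis refers to.** With p = 0.125, d = 0.05 and z = 1.96:

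n = z² p(1 − p)/d² = 3.8415 × 0.109375 / 0.0025 = 168.06.

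This reproduces the stated 168. It is a precision calculation for the incidence of DVT, which is closer to the rows of Table 8 than to its title. (The planned 100 against 168 is a separate matter.)

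**4. Why visit counts do not give the proportion.** Let a₁, a₈ and a₁₅ be the numbers of patients with an abnormal scan at each visit. The number with at least one abnormal scan, U, satisfies

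max(a₁, a₈, a₁₅) ≤ U ≤ min(N, a₁ + a₈ + a₁₅).

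With *assumed* counts of 2, 5 and 6 and N = 100:
- lower bound U = 6: 6%, exact 95% CI 2.2% to 12.6%;
- upper bound U = 13: 13%, exact 95% CI 7.1% to 21.2%.

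The exact limits are the Clopper-Pearson ones: lower = Beta quantile(0.025; x, N − x + 1), upper = Beta quantile(0.975; x + 1, N − x).

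The table would not say which bound applies, and U still counts any abnormal scan. How many of those patients had symptoms and needed intervention could be anything from 0 to U, and deaths or events not seen on Doppler would come on top.

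**5. Why the CI method should be named.** SAP 8.2.3 names none. At 0/100 the Wald interval is 0 to 0, with zero width; the exact upper limit is 1 − 0.025^(1/100) = 3.6%. At 2/100 Wald gives −0.7% to 4.7%; exact gives 0.2% to 7.0%.

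**The case against.** - **The SAP already names the variable.** This stands in part. SAP 8.2.1 and 8.2.3 specify a patient-level proportion with a CI, and Protocol 15.1 allows further tables as appropriate. A reader might infer that the primary proportion is not planned at all; the documents do not support that. What is missing is a shell or derivation rule, and the shell with the variable's name shows something else.
- **The Doppler may only confirm apparent DVT.** Protocol 6.3 and SAP 2.3 can be read so, which would bring an abnormal scan closer to symptomatic thrombosis. The Synopsis says all patients had it, and Table 8 calls it routine. The documents are mixed, but intervention, thrombotic death and a patient total are absent on either reading.
- **Tables 12 and 13 could show the components.** True: Protocol 15.3 treats DVT and PE as adverse events, and fatal events are serious. These tables could at most list them as event terms; they form no composite.
- **Table 8 will overstate the event rate.** A reader might infer this, perhaps by setting the 13 DVTs in 174 patients of the first correlative study (Protocol 4.2) against the absence of symptomatic thrombosis in the second. These are different studies and the second's size is not given, so the comparison estimates nothing here. Table 8 could add silent DVT and also omit stroke, infarction or death.
- **The study is descriptive, with no success threshold.** Correct: no pre-specified decision turns on this table. That limits the consequence but does not make the title fit the rows.

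**Conclusion.** Wrong as written. Completed as laid out, Table 8 would report Doppler findings by visit under the primary endpoint's name, and no shell or derivation rule would deliver the patient-level proportion that SAP 8.2.1 and 8.2.3 promise.

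Neither the size nor the direction of the effect in this trial can be derived from the documents. The 6% to 13% range rests on assumed visit counts and shows only that such counts do not determine the proportion.

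It may be tempting to conclude that DVT was really intended, or that the symptomatic endpoint was. The objective and the sizing basis point to DVT; SAP 4.1, 8.2.1 and the table title point to symptomatic thrombosis. The documents do not settle which side is the slip, and a correction is needed either way: if DVT is primary, the wording and title are wrong and the patient total is still missing.

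**What to change.** 1. Reconcile SAP 4.1, 8.2.1 and Table 8 with the DVT objective and the 12.5% sizing basis, and state which variable is primary.
2. Replace the Table 8 result rows with one patient-level line: n/N (%) with at least one event meeting the stated primary definition by Day 15, with an exact (Clopper-Pearson) 95% CI and the components. State the denominator and reconcile it with the study design text (Protocol 6, SAP 2), which speaks of patients whose data are complete and who were followed for two weeks.
3. On separate labelled lines, report patients with any Doppler-confirmed DVT by Day 15 and patients with symptomatic events, whichever is primary.
4. Move scan completeness and report sign-off to a data-quality table.

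**Cost.** One rewritten shell and one or two derived variables. Protocol 16.1 already asks for corrective treatment and outcome for each adverse event, so at most one CRF field for symptom status may be needed; the CRF is not shown. No scans or visits are added.
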